## 2. Study Objectives and Endpoints

### 2.1. Study Objectives

The overarching goal of this exploratory study is to investigate the safety and tolerability of NYX-783 in a Post-Traumatic Stress Disorder (PTSD) population, and to characterize the response profile of PTSD symptoms to NYX-783 treatment, as assessed by the intrusion, avoidance, and negative alterations in cognition and mood, and arousal & reactivity subscores as well as the total score on the Clinician-Administered PTSD Scale for the Diagnostic and Statistical Manual of Mental Disorders, 5th edition (CAPS-5)

#### 2.1.1. Primary Objective

The primary objective is to assess the effects of NYX-783 compared to placebo on reducing the severity of PTSD symptoms as measured by the Clinician-Administered PTSD Scale for the Diagnostic and Statistical Manual of Mental Disorders, 5th edition (CAPS-5).

### **2.1.2. Secondary Objectives**

The secondary objectives are

- To assess the effect of NYX-783 compared to placebo in the following outcomes: a) change in symptoms of PTSD as measured by the PTSD-Checklist for DSM-5 (PCL-5), b) change in sleep quality as measured by the Pittsburgh Sleep Quality Index (PSQI) Global Score, and c) change in cognitive function as measured by the Symbol Coding from the Brief Assessment of Cognition (BAC Symbol Coding).
- To assess the effect of NYX-783 compared to placebo in the change in global clinical severity of PTSD symptoms as measured by the Clinical Global Impressions-Severity (CGI-S) scale.
- To compare NYX-783 vs. placebo in the change in levels of anxiety and depression as measured by the Hospital Anxiety and Depression Scale (HADS).
- To assess the safety and tolerability of NYX-783 compared to placebo.

### **2.1.3. Exploratory Objectives**

The exploratory objectives are

## **2.2. Study Endpoints**

### **2.2.1. Efficacy Endpoints**

#### **2.2.1.1. Primary Efficacy Endpoint**

The primary efficacy endpoint of this study is the change in CAPS-5 total score and subscores following 4 weeks of treatment in each respective Stage (Stage 1 [baseline to Week 4] and Stage 2 [Week 4 to Week 8]). The primary endpoint will be evaluated using the weighted combination of the estimated treatment effects from stage-specific models.

[figure not shown]
#### **2.2.1.2. Secondary Efficacy Endpoint(s)**

The secondary efficacy endpoints of this study include the following

- Change in symptoms of PTSD as measured by the PCL-5 following 4 weeks of treatment in each respective Stage (Stage 1 [baseline to Week 4] and Stage 2 [Week 4 to Week 8])
- Change in sleep quality as measured by the PSQI Global Score and the PSQI Addendum for PTSD (PSQI-A) Global Score following 4 weeks of treatment in each respective Stage (Stage 1 [baseline to Week 4] and Stage 2 [Week 4 to Week 8])
- Change in cognitive function as measured by the Symbol Coding from BAC Symbol Coding following 4 weeks of treatment in each respective Stage (Stage 1 [baseline to Week 4] and Stage 2 [Week 4 to Week 8])
- Change in CGI-S following 4 weeks of treatment in each respective Stage
- Change in Hospital and Anxiety Depression Scale for Anxiety (HADS-A) and Hospital and Anxiety Depression Scale for Depression (HADS-D) subscores following 4 weeks of treatment in each respective Stage (Stage 1 [baseline to Week 4] and Stage 2 [Week 4 to Week 8])

#### **2.2.1.3. Exploratory Efficacy Endpoint(s)**

The exploratory efficacy endpoint of this study include the following:

## **2.2.2. Safety Endpoints**

### **2.2.2.1. Secondary Safety and Tolerability Endpoint(s)**

Safety and tolerability endpoints for this study will be based on: incidences of adverse events (AEs) and any changes in vital signs, physical examination findings (including weight), 12-lead ECG results, clinical laboratory values, and suicidality assessments (Sheehan Suicidality Tracking Scale [STS-S]).

## **3. Overall Study Design and Plan**

### **3.1. Overall Design**

### **3.2. Sample Size and Power**

Response to treatment will be measured using the CAPS-5 score change from baseline to Week 4 (Stage 1) and from Week 4 to Week 8 (Stage 2). If the effect size of NYX-783 is in line with the effect sizes observed in similar historical studies, this study is powered at approximately 80% to reject the null hypothesis at a one-sided  $\alpha = 0.10$  level for any single specified efficacy comparison. The sample size estimate (n=156) assumes a 15% dropout during Stage 1 and 11% dropout during Stage 2, based on the treatment comparisons specified for [Amendment 2](#) of the protocol. The sample size may be adjusted if the actual dropout rate exceeds this assumption; patients randomized based on earlier protocol versions will be included in data listings, but will not be included in data summaries or inferential analyses.

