### 14.3. Analysis Populations

**Intention-to-treat (ITT):** The ITT population will consist of all randomized subjects. Subjects in the ITT population will be analyzed according to the treatment they are assigned at randomization. The primary efficacy analysis will be performed on the ITT population. Unless otherwise specified, all other efficacy analyses also will be conducted on the ITT population.

Efficacy data for the 50 mg QW group will be summarized and shown in the listings but will not be included in the formal efficacy comparisons between treatment groups.

NOTE: Any additional study populations for analysis of efficacy will be defined in the SAP.

**Safety Population:** The safety population consists of all randomized subjects who receive at least one dose of study drug (active or placebo). Subjects in the safety population will be analyzed according to the treatment they actually received. Unless otherwise specified, all safety analyses will be conducted on the Safety population.

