## 5. Analysis Populations

The following analysis populations are planned for this study. As per protocol, the 50mg QW group will not be included in analysis population. Main efficacy and safety data for those subjects will be listed.

- **Safety Population (SAF):** The SAF consists of all randomized subjects who receive at least one dose of study drug (active or placebo). SAF inclusion and reporting will be evaluated separately for each Stage so there will be a safety set defined for Stage 1 (randomized subjects who receive at least one dose of study drug (active or placebo) during Stage 1 and a safety set defined for Stage 2 (randomized subjects who receive at least one dose of study drug (active or placebo) during Stage 2). Subjects in the SAF will be analyzed according to the treatment they actually received. For definition of actual treatment see Section [6.1.4](#). Unless otherwise specified, all safety analyses will be conducted on the Safety Population.
- **Intent-To-Treat (ITT) Population:** The ITT Population will consist of all randomized subjects. Subjects in the ITT Population will be analyzed according to the treatment they are assigned at randomization. The primary efficacy analysis will be performed on the ITT Population. Unless otherwise specified, all other efficacy analyses also will be conducted on the ITT Population. Subject data for each Stage is included in ITT analyses based on the availability of randomization assignments. As efficacy results are also presented by Stage, an ITT Stage 1 population will be created (all randomized subjects) and an ITT Stage 2 population will be created (all randomized subjects entering Stage 2).
- **Modified Intent-To-Treat (mITT) Population:** The mITT Population will consist of all ITT subjects who received at least 2 weeks of study drug and had at least one post-dose measurement of CAPS-5 (CAPS-5 questionnaire must be complete.) Subjects in the mITT Population will be analyzed according to the treatment they are assigned at randomization. This analysis population will serve as sensitivity analysis for primary efficacy analysis. As efficacy results are also presented by Stage, a mITT Stage 1 population will be created (all mITT subjects) and a mITT Stage 2 population will be created (all mITT subjects entering Stage 2).

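### The SAP confines earlier-version and 50 mg QW subjects to listings, safety included; the protocol bars QW only from formal efficacy comparisons, and SAP Section 11 declares neither departure

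*SAP*

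**What the plan says.** **Earlier protocol versions.** SAP Section 3.2 gives the sample size of 156 as "based on the treatment comparisons specified for" Amendment 2 of the protocol. It then says that "patients randomized based on earlier protocol versions will be included in data listings, but will not be included in data summaries or inferential analyses". It states no cut-off version or date and no restriction to efficacy.

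**The QW group.** SAP Section 5 opens its population definitions with "As per protocol, the 50mg QW group will not be included in analysis population", followed by "Main efficacy and safety data for those subjects will be listed". In the same section, "The ITT Population will consist of all randomized subjects", and the Safety Population (SAF) is every randomised subject who took any study drug. SAP Section 9 performs all safety analyses on the SAF.

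**The protocol.** Section 14.3 says "Efficacy data for the 50 mg QW group will be summarized and shown in the listings". The one restriction it then places on those data is narrower than the SAP's: "but will not be included in the formal efficacy comparisons between treatment groups". Its ITT and Safety definitions match the SAP's general ones and make no exception for a regimen or a protocol version. Section 14.10 uses the Safety Population for all safety variables. Section 14.10.1 asks for adverse event tables by treatment and overall.

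**Declared changes.** SAP Section 11 lists departures from the protocol's planned analysis. Neither exclusion is among them.

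**The concern.** Two SAP rules decide who is counted, and both are narrower than the protocol.

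The earlier-version rule cannot be applied together with the SAP's own ITT and SAF definitions. A programmer has to break one or the other. The QW rule claims protocol authority for something the protocol does not say, so a reader has little reason to look for a departure.

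Safety and tolerability belong to the study's overarching goal and are a secondary objective. If dosed subjects are outside the SAF, they are missing from the counts, denominators and rates for adverse events, serious adverse events, laboratory values and the suicidality scale. A table headed Safety Population would not then be the population the protocol defines. Likewise, a set headed ITT would not be all randomised subjects.

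**Working it through.** No disputed figure is involved. The one figure in SAP Section 3.2, about 80% power with 156 subjects, cannot be reproduced because the documents give no effect size, standard deviation or placebo non-response rate. Nothing here depends on it. The check is a comparison of the texts.

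**Step 1. Treatment of QW**

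| Item | Protocol | SAP |
|---|---|---|
| Formal efficacy comparisons | Excluded (14.3) | Excluded (5) |
| Efficacy summaries | Included (14.3) | Listed only (5) |
| ITT | All randomised, no exception (14.3) | Excluded (5) |
| Safety Population | All randomised and dosed, no exception (14.3) | Excluded (5) |
| Safety tables | All variables on the Safety Population (14.10) | All on the SAF (9), so QW is absent |

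The documents agree on the first row only. SAP Section 5 defines four populations: SAF, ITT, mITT and PP. QW is removed from 4 of 4.

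**Step 2. Treatment of earlier-version subjects.** Neither protocol Section 14.3 nor the definitions in SAP Section 5 mention protocol version. SAP Section 3.2 excludes these subjects from summaries and inference without limiting that to efficacy. The conventions at the end of SAP Section 6.1.4 reinforce this: data not analysed under the plan go to listings only and appear in no table or graph.

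**Step 3. The cut-off.** The preceding sentence in SAP Section 3.2 points to Amendment 2. SAP Section 1, however, says the SAP is written for Amendment 3, dated 01-May-2020. The protocol synopsis estimates enrolment from January 2019 to June 2020, which is 12 + 6 = 18 calendar months. January 2019 to April 2020 is 12 + 4 = 16 of them. Measured against Amendment 3, the rule would exclude anyone randomised in those 16 months. That is surely not intended, but the text does not rule it out.

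**Step 4. Declaration.** SAP Section 11 has five entries: the mITT population, the PCL-5 responder analysis, subgroups, the comparison of active groups together, and COVID-19. Entries covering either exclusion: 0 of 5.

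**Step 5. Reach into the primary test.** The current design has arms [1] to [11], all placebo or once daily (QD), so QW is in 0 of 11. The primary test uses arms 1, 2, 3, 7, 8 and 9, so QW is in 0 of 6. Excluding QW does not touch the primary comparison. Excluding earlier-version subjects could do so only if earlier versions randomised people to placebo or to a QD dose that was kept. The documents do not say.

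**Step 6. What would follow from simply returning QW to the SAF.** The actual-treatment rule in SAP Section 6.1.4 ranks 50 mg, 10 mg and placebo only, and the safety columns in SAP Section 4.1 contain no QW. Without a QW level, weekly 50 mg subjects would fall into the daily 50 mg column. Any repair must therefore change those two places as well.

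**The case against.** The strongest reply is that this is one documentation lapse about a dropped regimen.

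- **The two groups may be the same people.** This is possible. Each rule would still be wrong as written, and the wording of Section 3.2 would also cover placebo and QD subjects if there were any.
- **Section 3.2 is about sample size and never mentions safety.** This is true, and its reach into safety rests on unqualified wording. But that wording covers data summaries without limit, and a rule deciding who is counted should not depend on its heading. For QW, Section 5 names safety data explicitly.
- **A SAP may add detail, and the populations carry an escape clause.** In both documents that clause qualifies which analyses use a population, not who belongs to it. The protocol lets the SAP define additional efficacy populations. It does not let it shrink the Safety Population or drop a promised summary.
- **The by-treatment request in protocol Section 14.10.1 does not name QW.** This is fair. It is supporting evidence only, and the point rests on Section 14.3.
- **Nothing is concealed or lost.** Both exclusions are stated openly, all adverse events are displayed in listings, and the safety board's monitoring is separate from these tables. All of this stands. What is missing is a place in the tabulated counts and rates, and a declaration.
- **No number of affected subjects is given.** This also stands, and it limits the severity. Still, both rules presuppose that such subjects may exist.

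**Conclusion.** The concern holds. The SAP confines both groups to listings, safety included. The protocol keeps QW out of the formal efficacy comparisons only, makes no exception by protocol version, and is wrongly cited as authority for the QW exclusion. SAP Section 11 records neither departure.

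In terms the documents allow, QW is removed from 4 of 4 SAP populations and 0 of 5 declared changes cover either exclusion. The number of subjects affected is unknown, so no size of effect on safety rates is claimed, and none on power or the primary result. The safety consequence rests on reading Section 3.2 as written and on at least one such subject having been dosed. This should be fixed before unblinding; it does not by itself undermine the primary analysis.

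**What to change.** Before unblinding:

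1. Limit the exclusions in SAP Sections 3.2 and 5 to the formal efficacy comparisons, and state the Section 3.2 cut-off by amendment number and date.
2. Keep every dosed subject in the SAF and the safety tables, with 50 mg QW in its own column. Add a QW level to the actual-treatment rule in Section 6.1.4 and to the column list in Section 4.1.
3. Summarise QW efficacy descriptively, as protocol Section 14.3 provides, and correct the attribution to the protocol in SAP Section 5.
4. If any earlier-version placebo or QD subjects stay out of the primary test, name that set as a modified population and declare it with a reason in SAP Section 11. A sensitivity analysis including them is optional and depends on the earlier design.

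A lighter course is to keep both exclusions but declare and justify them in Section 11, correct the attribution and name the cut-off. That cures the silence, but the safety tables would still not match the protocol's Safety Population, so it is second best.

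The cost is wording in SAP Sections 3.2, 5 and 11, one derivation level, a QW column in the safety tables and one descriptive QW efficacy summary. Because safety tables are produced by stage and the earlier stage structure is not documented, the table layout may need slightly more work than a single column.

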### **3.3. Study Population**

The study population consists of adult subjects diagnosed with Post-Traumatic Stress Disorder (PTSD). The goal of the study is to recruit subjects with a clearly identifiable primary traumatic event during adulthood.

### **3.4. Treatments Administered**

[figure not shown]
NYX-783 is formulated for this study as 50 mg, and 10 mg capsules for oral administration. Matching placebo capsules for oral administration are also provided. The study will be conducted as a placebo-controlled, double-blind study. The Treatment period will be conducted in 2 Stages to examine the efficacy and safety of NYX-783 compared to placebo in the treatment of PTSD symptoms.

### **3.5. Method of Assigning Subjects to Treatment Groups**

On Day 1, subjects will be randomized to receive placebo, NYX-783 50 mg QD, or NYX-783 10 mg QD in a 4:1:1 ratio, respectively. Placebo responders and placebo non-responders (CAPS-5 total score reduction from baseline  $\leq 35\%$  and total CAPS-5 total score  $\geq 26$  at Week 4) will be identified at the completion of Stage 1 (Weeks 1-4) in a blinded fashion; then, each group (i.e., placebo responders and placebo non-responders) will be re-randomized in a blinded fashion to placebo, NYX-783 50 mg QD, NYX-783 10 mg QD in a 3:2:2 ratio, respectively, for Stage 2 (Weeks 4-8).

treatment. Subjects who received active treatment during Stage 1 will receive placebo in Stage 2.

**Figure 1: Study Design**

\* Placebo non-responder: CAPS-5 reduction from baseline ≤ 35% and CAPS-5 total score ≥ 26 at Week 4.

BAC Symbol Coding, Symbol Coding from the Brief Assessment of Cognition; CAPS-5, Clinicians Administered PTSD Scale for DSM-5; [REDACTED] CGI-S, CGI-Severity; HADS, Hospital Anxiety and Depression Scale; LEC-5, Life Events Checklist for DSM-5; PCL-5, PTSD Checklist for DSM-5; PSQI, Pittsburgh Sleep Quality Inventory; PSQI-A, PSQI-Addendum for PTSD; SCID-5, Structured Interview for DSM-5; [REDACTED] S-STS, Sheehan Suicidality Tracking Scale. ☎ Phone Interview

Figure from protocol Section 7.1 Overall Study Design and Plan: Description.

### 3.6. Blinding and Unblinding

The study will be conducted as a placebo-controlled, double-blind study. The authorized investigative site personnel will obtain blinded kit assignments using an interactive response technology (IRT) system. The blinded dose information may only be obtained by the investigator (or designee) in an emergency, where the information may have an impact on further treatment decisions or aid in the emergency treatment of the subject.

### 3.7. Schedule of Events

A detailed schedule of events for the study is provided in [Table 1](#)

**Table 1: Schedule of Events**

Phases/Visits Tasks / Events	Screening		Double-blind Treatment Phase					Early Termination	Safety Follow-Up
	Visit 1 Screening	SAFER	Day 1	Week 2	Week 4	Week 6	Week 8		
			Stage 1		Stage 2				
Days relative to start dosing of study drug	-21 to -7	-7 a	1	14 a	28 a	42 a	56 a	NA	63 ap
ENTRY / SAFETY/ ADMINISTRATIVE									
Informed consent	X								
Inclusion/exclusion criteria	X	X i	X						
Demographics / habits b	X								
Medical/psychiatric history	X		X						
PTSD diagnosis (CAPS-5)	X	X i							
SAFER interview (Confirmation of PTSD diagnosis and overview of inclusion/exclusion criteria)		X i							
LEC-5 (Part of PCL-5 with LEC-5 and Criterion A)	X								
S-STS	X s		X u	X u	X u	X u	X u		
Vital signs c	X		X	X	X	X	X	X r	
Height	X e								
Weight	X e		X	X	X	X	X	X r	
Physical examination	X				X		X	X	X r
12-lead ECG d	X		X		X		X	X	X r
Randomization			X		X				
Prior and concomitant medications	X		X	X	X	X	X	X	X
Study drug dispensing e			X	X	X	X			
Study drug administration			X k	X	X l	X	X		
Study drug compliance monitoring f			X	X	X	X	X	X	
Adverse events g	X	X	X	X	X	X	X	X	X
LABORATORY TESTS									
Clinical chemistry g	X		X	X	X	X	X	X r	
Hematology	X		X		X		X	X	X r
HIV and hepatitis tests	X								

Pregnancy test v	X h		X i		X i		X i	X i
Drug and alcohol screen	X h		X i		X i		X h	X h
Urinalysis	X		X		X		X	X
Clinical Measures								
CAPS-5	X s		X t					
PCL-5	X s		X t					
HADS t	X		X	X	X	X	X	
CGI-S	X		X	X	X	X	X	
PSQI	X		X	X	X	X	X	
PSQI-A	X		X	X	X	X	X	
DES-II			X		X		X	
BAC-Symbol Coding			X		X		X	

Abbreviations: BAC-Symbol Coding = Symbol Coding from the Brief Assessment of Cognition; CAPS-5 = Clinician Administered PTSD Scale for DSM-5; [REDACTED] CGI-S = Clinical Global Impression – Severity; DES-II = Dissociative Experiences Scale-II; DNA = Deoxyribonucleic acid; ECG = electrocardiogram; HADS = Hospital Anxiety and Depression Scale; HIV = human immunodeficiency virus; LEC-5 = Life Events Checklist for DSM-5; [REDACTED] PCL-5 = PTSD Checklist for DSM-5; [REDACTED] PSQI = Pittsburgh Sleep Quality Index; PSQI-A = Pittsburgh Sleep Quality Index Addendum; PTSD = Post-Traumatic Stress Disorder; SCID-5-CT = Structured Clinical Interview for DSM-5 (Clinical Trials Version); [REDACTED] = Sheehan Suicidality Tracking Scale.

- a) Visit window is  $\pm 3$  days.
- b) Includes alcohol or illicit drug use history, employment status, smoking history, and index traumatic event.
- c) Collect vital signs after at least 5 minutes of rest, seated or supine.
- d) ECG after at least 5 minutes supine rest.
- e) Include body mass index calculation.
- f) Subjects use smartphone video application monitoring. Investigative site personnel calculate compliance and document accountability via capsule count/blister package inspection.
- g) Serious Adverse Event (SAE) reporting begins at time of informed consent and continues until 30 days after the last dose of study drug. Non-serious AE collection commences with the time of first dose of study drug until last day of subject participation in the study.
- h) Serum sample.
- i) Urine sample or breathalyzer (alcohol screen).
- j) Via phone.
- k) Doses are to be administered at the clinic on Day1 (after completing other procedures) then on an outpatient basis.

## 4. Statistical Analysis and Reporting

### 4.1. Introduction

Data processing, tabulation of descriptive statistics, calculation of inferential statistics, and graphical representations will be performed primarily using SAS (release 9.4 or higher).

Continuous (quantitative) variable summaries will include the number of subjects (n) with non-missing values, mean, standard deviation (SD) (or standard error (SE) if appropriate), median, minimum, and maximum. Confidence intervals (CIs) will be added if appropriate.

Categorical (qualitative) variable summaries will be based on frequencies and percentages.

Unless stated otherwise, efficacy data for endpoints included in mixed effects repeated measures model (MMRM) analyses (groups [1], [2], [3], [7], [8], and [9]) will be summarized by visit and treatment group (Placebo, NYX-783 10 mg QD, NYX-783 50 mg QD) to allow for summary data treatment comparisons as per model inference.

Efficacy data for Stage 2 groups [4], [5], [6], [10], and [11] will be presented separately.

Unless stated otherwise, safety data will be summarized by Stage and treatment group (Placebo [as Placebo Only and Placebo Stage 2, separately], NYX-783 10 mg QD, NYX-783 50 mg QD); data presented by visit will be displayed based on the treatment group which applies at onset for AEs/collection date.

The minimum and maximum will be reported with the same degree of precision (i.e., the same number of decimal places) as the observed data. Measures of location (mean and median) will be reported to 1 degree of precision more than the observed data and measures of spread (SD, SE) will be reported to 2 degrees of precision more than the observed data.

Percentages will be presented to 1 decimal place, unless otherwise specified.

Unless otherwise indicated, all statistical tests will be conducted at a 0.10 significance level using one-sided tests and p-values will be reported. Corresponding 80% CIs (the interpretation of which is equivalent to a one-sided 90% CI when restricted to a single bound) will be presented.

